To assess the safety and tolerability profile of durvalumab monotherapy and durvalumab and tremelimumab combination therapy compared to placebo in patients with LS-SCLC	AEs; laboratory findings including clinical chemistry, hematology, and urinalysis; physical examinations; vital signs including blood pressure and pulse; and electrocardiograms	

Exploratory objectives:	Endpoints/variables:	
To assess treatment-related side effects in patients treated with durvalumab monotherapy and durvalumab and tremelimumab combination therapy compared to placebo using PRO-CTCAE	Change in the 9 treatment-related symptoms evaluated in this study	
To assess the patients' overall impression of the severity of their cancer symptoms using PGIS	PGIS: Proportion of patients assessing current symptom severity	
To describe and evaluate health resource use associated with durvalumab monotherapy and durvalumab and tremelimumab combination therapy and underlying disease	d hospitalization, outpatient visits, or emergency	
To explore the impact of treatment and disease state on health state utility using the EQ-5D-5L	The EQ-5D-5L health state utility index will be used to derive health state utility based on patient-reported data	
To collect blood and tissue samples, or leverage residual samples, for analysis of peripheral and tumoral biomarkers (not applicable for China)	Exploratory biomarkers, which may include but are not limited to, DNA, RNA, and protein-based assessment within the tumor microenvironment and/or in the periphery. Evaluation of tumor-cell and/or immune-cell gene expression profiles, tumor or ctDNA-derived mutational analyses, PD-L1 expression, SCLC molecular subtypes, tumor-immune spatial profiling, etc., and association of biomarkers with response and/or resistance	
To investigate the relationship between TMB measured in tumor and/or blood and efficacy outcomes with durvalumab monotherapy and durvalumab and tremelimumab combination therapy (TMB-related testing or analysis will not be conducted on samples from China)	TMB relative to response/efficacy outcomes (ORR, PFS, and OS)	
To explore the relationship(s) between patient biomarker status and durvalumab PK exposure and clinical outcomes before and after treatment (TMB related testing or analysis will not be conducted on samples from China)	Biomarker status before and after treatment, durvalumab PK exposure, and relationship with clinical outcomes, efficacy, AEs, and/or safety parameters, as deemed appropriate	

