#### 9.4.5 Calculation or derivation of PRO-CTCAE

PRO-CTCAE data will be presented using summaries and descriptive statistics based on the Full Analysis Set and further details will be provided in the SAP.

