3.3.4 PRO-CTCAE

The PRO-CTCAE is included to address tolerability from the patient's perspective. It was developed by the National Cancer Institute (NCI). The PRO-CTCAE will only be administered in English, German, Spanish and Japanese. In countries where a linguistically validated version does not exist, the English version is administered for patients who signed English informed consent. The PRO-CTCAE was developed in recognition that collecting treatment-related symptom data directly from patients using PRO tools can improve the accuracy and efficiency of symptomatic AE data collection. This was based on findings from multiple studies demonstrating that physicians and nurses underestimate treatment-related symptom onset, frequency, and severity in comparison with patient ratings (Basch et al 2009, Litwin et al 1998, Sprangers and Aaronson 1992). These treatment-related symptoms have been converted to patient terms (e.g. the CTCAE term "myalgia" has been converted to "aching muscles"). For several symptoms, like fatigue and pain, additional questions are asked about the frequency, severity, and interference with usual activities. The items included in the PRO-CTCAE have undergone extensive qualitative review among experts and patients. These items have been extensively evaluated by cancer subjects to be clear, comprehendible, and measure the symptom of interest. For this study, 9 symptoms are considered relevant for this cancer treatment: swallowing, nausea, heartburn, diarrhea, wheezing, rash, itchy skin, skin burns from radiation and headache (see CSP Appendix H).

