3.3.5 PRO compliance rates

Summary measures of overall compliance and compliance over time will be derived for the EORTC QLQ-C30, LC13 and EQ-5D-5L respectively. These will be based upon:

- Received questionnaire = a questionnaire that has been received and has a completion date and at least one individual item completed.
- Expected questionnaire = a questionnaire that is expected to be completed at a scheduled assessment time e.g. a questionnaire from a patient who has not withdrawn from the study at the scheduled assessment time but excluding patients in countries with no available translation. Date of study discontinuation, PFS2 or death will be mapped to the nearest visit date to define the number of expected forms.
- Evaluable questionnaire = a questionnaire with a completion date and at least one subscale that is non-missing.
- Overall PRO compliance rate is defined as: Total number of evaluable questionnaires across all time points, divided by total number of questionnaires expected to be received across all time points multiplied by 100.
- Overall patient compliance rate is defined for each randomized treatment group as: Total number of patients with an evaluable baseline and at least one evaluable follow-up questionnaire (as defined above), divided by the total number of patients expected to have completed at least a baseline questionnaire multiplied by 100.

Compliance over time will be calculated separately for each visit, including baseline, as the number of patients with an evaluable questionnaire at the time point (as defined above), divided by number of patients still expected to complete questionnaires. Similarly, the evaluability rate over time will be calculated separately for each visit, including baseline, as the number of evaluable questionnaires (per definition above), divided by the number of received questionnaires.

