Endpoints Analyzed	Notes
Objective response rate	Cochran-Mantel-Haenszel (CMH) test for difference in proportions using BICR assessments (RECIST 1.1) adjusting for the same factors as the primary endpoint for:
	 Secondary analysis (durvalumab monotherapy and durvalumab + tremelimumab combination therapy versus placebo and durvalumab monotherapy versus durvalumab + tremelimumab)
	Sensitivity analysis using CMH test repeated using the site Investigator assessments (RECIST 1.1)
Duration of response	Kaplan-Meier estimates and confidence intervals
PFS at 18 months and 24 months	Kaplan-Meier estimates and confidence intervals
Time to death or distant metastasis	Stratified log-rank test using BICR assessments (RECIST 1.1)
OS at 24 and 36 months	Kaplan-Meier estimates of survival at 24 months and 36 months and analyses following the method described by Klein et al (Klein et al 2008, Klein et al 2007)
Time from randomization to second progression	Stratified log-rank test using site Investigator assessments
Change from baseline in key symptoms (EORTC QLQ-C30 and QLQ-LC13)	Mixed-model repeated measures analysis
GHS/QoL/Function improvement rate (EORTC QLQ-C30 endpoints)	Logistic regression
Symptom improvement rate (EORTC QLQ-C30 and QLQ-LC13 endpoints)	Logistic regression
Time to GHS/QoL/Function deterioration (EORTC QLQ-C30 endpoints)	Stratified log-rank test
Time to symptom deterioration (EORTC QLQ-C30 and QLQ-LC13 endpoints)	Stratified log-rank test
Treatment-related symptoms (PRO-CTCAE and PGIS)	Presented using summaries and descriptive statistics

BICR Blinded Independent Central Review; CTCAE Common Terminology Criteria for Adverse Event; EORTC European Organisation for Research and Treatment of Cancer; GHS/QoL Global health score/Quality of life; ORR Objective response rate; OS Overall survival; PFS Progression-free survival; PGIS Patient's Global Impression of Severity; PRO Patient-reported outcome; QLQ-C30 30-Item core quality of life questionnaire; QLQ-LC13 Lung cancer module.

[figure not shown]

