Symptom, functional and GHS/QoL improvement rates will be analyzed by comparing between treatment groups using a logistic regression model adjusting for the same factors as the PFS endpoint. The results of the analysis will be presented in terms of an odds ratio together with its associated profile likelihood 95% CI and p-value (based on twice the change in log-likelihood resulting from the addition of a treatment factor to the model). The odds ratio and 95% CI for each scale/item will be presented graphically on a forest plot. If there are very few responses in 1 treatment group, a Fisher's exact test will be considered.

Change from baseline

Summaries of original and change from baseline values of each symptom scale/item, the GHS/QoL score, and each functional domain will be reported by assessment timepoint for each treatment group. Graphical presentations may also be produced as appropriate. Summaries of the number and percentage of patients in each response category at each assessment timepoint for each ordinal item (in terms of the proportion of patients in the categories of improvement, no change, and deterioration as defined in Table 6) will also be produced for each treatment group.

A summary of compliance rate and evaluability rate will be provided for each treatment group, by assessment time point and also for overall. The summary will be provided for the FAS, combination analysis set, and patients who have discontinued treatment.

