4.2.11.2 EQ-5D-5L

Descriptive statistics will be calculated for each scheduled time point in the study, for each treatment group and as a total. These will report the number of patients, the number of EQ-5D-5L questionnaires completed at each visit, the number and proportion responding to each dimension of the EQ-5D-5L. Additionally, summary statistics will be reported for the EQ-5D-5L index score and the EQ-5D-5L VAS score, and the change from baseline for the index and VAS scores.

A summary of compliance rate and evaluability rate will be provided for each treatment group, by assessment time point and overall.

To support submissions to payers, additional analyses may be undertaken, and these will be outlined in a separate Payer Analysis Plan.

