4.2.11.4 PRO-CTCAE

The number and percentage of patients in each category of the responses for each PRO-CTCAE item will be summarized by treatment group and assessment time point.

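### The PRO-CTCAE endpoint is worded as change, but the only planned table cannot show how many patients worsened from their own baseline (minor, exploratory)

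*SAP*

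**What the plan says.** Protocol section 3 (Table 3) gives the exploratory PRO-CTCAE endpoint as "Change in the 9 treatment-related symptoms evaluated in this study", and SAP 1.1.4 uses the same words. Protocol 9.4.5 promises descriptive summaries "based on the Full Analysis Set and further details will be provided in the SAP".

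In the SAP, section 3.3.4 lists the nine symptoms and the language restriction ("The PRO-CTCAE will only be administered in English, German, Spanish and Japanese", with a provision for patients who consented in English elsewhere). It defines no change variable and no rule for worsening. Table 7 in SAP 4.2 says only "Presented using summaries and descriptive statistics". Section 4.2.11.4 is a single sentence: "The number and percentage of patients in each category of the responses for each PRO-CTCAE item will be summarized by treatment group" and time point.

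The neighbouring sections go further. For the EORTC questionnaires, SAP 4.2.11.1 plans "Summaries of original and change from baseline values of each symptom scale/item", and for EQ-5D-5L, SAP 4.2.11.2 plans "the change from baseline for the index and VAS scores".

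**The concern.** SAP 3.3.4 includes PRO-CTCAE to capture tolerability as the patient sees it. The natural question is how many patients on each arm developed a symptom, or had one get worse, after starting treatment. Category percentages at successive visits do not answer it, because improvement in some patients can cancel worsening in others.

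That cancellation is plausible here. Patients enter within 1 to 42 days of finishing chemoradiotherapy, and exclusion criterion 11 bars only unresolved toxicity of Grade 2 or above, with exceptions, so milder residual symptoms are allowed at baseline. The nine symptoms mix ones that may be resolving after chemoradiotherapy (swallowing difficulty, radiation skin burns) with ones that may newly appear on an immune checkpoint inhibitor (rash, itching, diarrhea). A flat column of percentages could mean that nothing happened, or that recovery and new onset happened together. At stake is how well a descriptive tolerability display can be read. No hypothesis test is involved.

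**Working it through.** The plan states no PRO-CTCAE figure to reproduce. The check is a comparison of text, followed by a short piece of arithmetic on assumed values.

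**1. Endpoint wording against planned summary**

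- PGIS: the endpoint is a proportion of patients by severity, and SAP 4.2.11.3 tabulates response categories. These match.
- EORTC: the endpoint is change, and SAP 4.2.11.1 summarizes change from baseline and the improved/no change/deteriorated categories of Table 6. These match.
- EQ-5D-5L: the endpoint is a utility index, not worded as change, yet SAP 4.2.11.2 still summarizes change from baseline.
- PRO-CTCAE: the endpoint is change, and SAP 4.2.11.4 tabulates response categories only. There is no patient-level change.

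**2. Does a general rule fill the gap?** SAP 4.1.1 says how change is calculated where it is used; it adds no table. SAP 4.2.13 allows further safety summaries but commits to none. SAP section 6, on changes from the protocol, does not mention PRO-CTCAE.

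**3. Are the data there?** Yes. The ePRO footnote to Protocol Table 1 has baseline questionnaires completed in clinic on Cycle 1 Day 1 before dosing.

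**4. What category percentages can and cannot tell.** Take a yes/no item such as rash, answered by the same patients twice. Let p0 be the share with the symptom at baseline, p1 the share later, w the share going from No to Yes, and i the share going from Yes to No. Then p1 = p0 + w − i, so the table fixes only w − i. The share who worsened is bounded by

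max(0, p1 − p0) ≤ w ≤ min(p1, 1 − p0).

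The documents give no symptom prevalence, so these inputs are assumed:

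| p0 | p1 | lowest w | highest w |
|---|---|---|---|
| 10% | 10% | 0% | 10% |
| 20% | 20% | 0% | 20% |
| 20% | 30% | 10% | 30% |
| 30% | 30% | 0% | 30% |
| 50% | 50% | 0% | 50% |

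The same holds for a graded item. Suppose all of a planned arm of 262 answered, with 131 reporting none and 131 reporting mild at both times. The table is identical if nobody changed, or if 131 worsened (131/262 = 50%) and the other 131 improved.

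**5. How many time points?** Protocol Table 1 has PRO-CTCAE weekly for 12 weeks and then every 4 weeks. Taking 24 months as 104 weeks gives 12 + (104 − 12)/4 = 12 + 23 = 35 post-baseline time points. This bears on how large the fix should be.

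**The case against.** The best defence is that the SAP delivers what was promised. The endpoint does not say within-patient change, Protocol 9.4.5 asks only for descriptive summaries, and category distributions by visit, with baseline beside them, do describe change for the group. This stands in part. A reader might infer that the SAP breaks a protocol commitment or shows no change at all, and the documents support neither. What is missing is the patient-level count.

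A second defence is overlap. Swallowing, nausea and diarrhea are also covered by QLQ-C30 or QLQ-LC13, which get change from baseline and time to deterioration. Treatment-emergent adverse events count worsening from the last pre-dose grade. Protocol 9.5.1 says all data collected will be listed. This narrows the gap but does not close it. Heartburn, wheezing, rash, itching, radiation burns and headache have no such EORTC summary, adverse events are graded by the investigator, and a listing is not a count.

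A third defence is that the upper bounds above are extreme. At 50% and 50%, the top of the range needs every symptomatic patient to recover and every other patient to become symptomatic. That is fair: the bounds show what the table leaves open and do not estimate what will happen.

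**Conclusion.** The point holds as a small improvement, at the low end of minor. The planned table shows group-level shifts but not how many patients worsened from their own baseline, although the endpoint is worded as change and the baseline is collected. The size depends on unknown prevalences; on the assumed values above, the undetermined range is 10 to 50 percentage points wide. The reading assumes that the by-visit table includes baseline, which SAP 4.2.11.4 does not state.

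The endpoint is exploratory and descriptive, it is outside the multiple testing procedure, and SAP 1.1.4 allows exploratory objectives to be reported outside the clinical study report. No alpha, power or primary result is touched.

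A reader might also infer that the table conceals who stopped answering, especially as SAP 3.3.5 says "Summary measures of overall compliance and compliance over time will be derived for the EORTC QLQ-C30, LC13 and EQ-5D-5L respectively" and does not name PRO-CTCAE. The documents do not support making that part of this point. The planned table gives counts as well as percentages, so summing the categories shows how many answered at each visit, and SAP 4.1 by default takes percentages out of the population total. Only completion against expected forms is not summarized. Death and drop-out would also affect a paired shift table, so they are not evidence for preferring one.

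**What to change.** Keep the planned table. Add to SAP 4.2.11.4, for each item, one shift table by arm from baseline to worst post-baseline response. It should give the number and percentage worse than their own baseline among patients with a baseline and at least one post-baseline response. State that denominator in the table, because the SAP's default denominator would otherwise include patients never offered the questionnaire.

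Two item rules are needed. For rash, count No to Yes. For the radiation-burn item, treat Not applicable as missing.

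If change over time is wanted as well, limit a by-visit version to a few selected visits, subject to the 20-observation rule in SAP 4.1.2. A full shift at all 35 time points for every item would be bulkier than the question deserves.

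The cost is SAP wording and some further descriptive tables from data already collected. There are two drawbacks. Denominators will be small in a language-restricted subset. A worst-value summary also depends on length of follow-up, since an arm followed for longer has more chances to record a bad week; it should be read beside the by-visit table.

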4.2.12 Health care resource use

The potential impact the disease and treatment have on health care resource use will be analyzed for the purposes of submissions to payers. Descriptive statistics (as appropriate, including means, median, ranges or frequencies and percentages) will be provided for each treatment group on the different types of hospital admissions, the length of stay of people admitted in to hospital for at least one overnight stay and length of stay of people admitted to intensive care / high dependency units, as well as the primary sign or symptom the patient presents with. To support submissions to payers, additional analyses may be undertaken, and these will be outlined in a separate Payer Analysis Plan.

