- See Section 8.1 and Appendix F for additional details relevant to the imaging schedule. The follow-up scan after a RECIST 1.1-defined PD is also evaluated according to RECIST 1.1 criteria (Appendix F).
- m Health resource use assessment should be performed every 24 weeks (±2 weeks) after treatment discontinuation and until PFS2 or study termination or death, whichever occurs first.

ADA Anti-drug antibody; AE Adverse event; CT Computed tomography; CTCAE Common Terminology Criteria for Adverse Events; DCO Data cut-off; ECOG Eastern Cooperative Oncology Group; eCRF Electronic case report form; EORTC European Organisation for Research and Treatment of Cancer; ePRO Electronic patient reported outcome; EQ-5D-5L EuroQoL 5 dimension, 5 level health state utility index; IP Investigational product (ie, durvalumab, tremelimumab, or placebo); LS-SCLC Limited stage small-cell lung cancer; MRI Magnetic resonance imaging; PFS2 Time from randomization to second progression; PGIS Patient's Global Impression of Severity; PK Pharmacokinetic; PRO Patient-reported outcome; QLQ-C30 30 Item core quality of life questionnaire; QLQ LC13 Lung cancer module; qXw Every X weeks; RECIST Response Evaluation Criteria In Solid Tumors; SAE Serious adverse event; T3 Triiodothyronine; T4 Thyroxine; TSH Thyroid-stimulating hormone; WHO World Health Organization.

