#### 8.9 Health Economics

For the purposes of economic evaluation, it is necessary to capture health care resource use related to the treatment and the underlying disease. Within the study, the following will be captured:

- Hospital episodes including the type of contact (hospitalizations, outpatient, or day case), reason, length of stay by ward type (including intensive care unit), and concomitant medications and procedures
- Treatment related to AEs (including the method of delivery of the treatment)
- Treatment not related to the study

The above resource use data will mainly come from the patient's medical record and will be captured in the eCRF.

The assessment of health economic resource use data will provide important information for payers and will be used within economic evaluations of durvalumab.

Frequency and estimates of resource use, including length of stay and number of hospital admissions, will be derived from the health resource use information.

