#### 9.5.1.10 Health care resource use

An exploratory health economic analysis of hospital episodes including type of contact (hospitalization, outpatient, and day case), reason, length of stay by ward type (including intensive care unit), and procedures and tests may be undertaken to examine the impact of disease and treatment on resource use to primarily support the economic evaluation of durvalumab monotherapy and the durvalumab and tremelimumab combination therapy. This would include providing descriptive statistics as appropriate, including means, median, and ranges.

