1.1.4 Exploratory objectives

Exploratory objectives*:	Endpoint/variables:
To assess treatment-related side effects in patients treated with durvalumab monotherapy and durvalumab and tremelimumab combination therapy compared to placebo using PRO-CTCAE	Change in the 9 treatment-related symptoms evaluated in this study
To assess the patients' overall impression of the severity of their cancer symptoms using PGIS	PGIS: Proportion of patients assessing current symptom severity
To describe and evaluate health resource use associated with durvalumab monotherapy and durvalumab and tremelimumab combination therapy and underlying disease	Health resource utilization measures including hospitalization, outpatient visits, or emergency department visits
To explore the impact of treatment and disease state on health state utility using the EQ-5D-5L	The EQ-5D-5L health state utility index will be used to derive health state utility based on patient-reported data

Exploratory objectives*:

To collect blood and tissue samples, or leverage residual samples, for analysis of peripheral and tumoral biomarkers (not applicable to China)

To investigate the relationship between TMB measured in tumor and/or blood and efficacy outcomes with durvalumab monotherapy and durvalumab and tremelimumab combination therapy (TMB-related testing or analysis will not be conducted on samples from China)

To explore the relationship(s) between patient biomarker status and durvalumab PK exposure and clinical outcomes before and after treatment (TMB related testing or analysis will not be conducted on samples from China)

To explore irRECIST as assessment methodologies for clinical benefit of durvalumab monotherapy and durvalumab and tremelimumab combination therapy compared to placebo with assessment by BICR

To collect and store DNA from tissue and/or blood according to each country's local and ethical procedures for future exploratory research into genes/genetic variation that may influence response (i.e. distribution, safety, tolerability, and efficacy) to IPs and/or susceptibility to disease (optional, not applicable for China)

To investigate the effect of baseline colonic microbiome on response to treatment and the effect of treatment on the microbiome over time (applicable for EU and North America only)

Endpoint/variables:

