3.7 Health Care Resource Use

To investigate the impact of treatment and disease on health care resource, the following variables will be captured:

- Planned and unplanned hospital attendances beyond trial protocol mandated visits (including physician visits, emergency room visits, day cases and admissions)
- Primary sign or symptom the patient presents with
- Length of hospital stay
- Length of any time spent in an intensive care unit (ICU)

The length of hospital stay will be calculated as the difference between the date of hospital discharge (or death date) and the start date of hospitalization or start of study drug if the start of study drug is after start date of hospitalization (length of hospital stay = end date of hospitalization - start date of hospitalization + 1). Patients with missing discharge dates will be calculated as the difference between the last day with available data and the start date of hospitalization. The length of ICU stay will be calculated using the same method.

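### SAP 4.2.12 summarizes hospital admissions per arm without observation time, although HOSPAD collection ends at PFS2, so a PFS2 difference alone would shift admission counts and the share ever admitted

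*SAP*

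**What the plan says.** **Collection.** Protocol Table 1 schedules HOSPAD every 24 weeks until treatment discontinuation. Footnote m to Table 2 then continues it "every 24 weeks (±2 weeks) after treatment discontinuation and until PFS2 or study termination or death, whichever occurs first".

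**Endpoint and variables.** The exploratory endpoint in SAP 1.1.4 is "Health resource utilization measures including hospitalization, outpatient visits, or emergency department visits". SAP 3.7 captures "Planned and unplanned hospital attendances beyond trial protocol mandated visits (including physician visits, emergency room visits, day cases and admissions"), together with presenting sign or symptom, length of stay and ICU time.

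**Analysis.** SAP 4.2.12 plans "Descriptive statistics (as appropriate, including means, median, ranges or frequencies and percentages") and states that these "will be provided for each treatment group on the different types of hospital admissions, the length of stay of people admitted in to hospital"; the length-of-stay summary is limited to overnight stays. It adds length of ICU or high-dependency stay and the presenting sign or symptom. The stated purpose is submissions to payers, and further analyses may go into a separate Payer Analysis Plan.

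**Protocol counterpart.** Section 8.9 says "Frequency and estimates of resource use, including length of stay and number of hospital admissions, will be derived" from the resource use information. Section 9.5.1.10 describes an optional exploratory analysis of "hospital episodes including type of contact (hospitalization, outpatient, and day case), reason, length of stay by ward type", with descriptive statistics.

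None of these four sections (SAP 3.7 and 4.2.12, Protocol 8.9 and 9.5.1.10) names a person-time denominator or a common observation window. The SAP does use one elsewhere: SAP 4.2.13.1 reports adverse event rates per 100 patient-years.

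**The concern.** A patient stops contributing HOSPAD data at second progression or death. Both are outcomes that treatment is meant to delay. A count of admissions per arm, a mean per patient, or a percentage ever admitted therefore reflects two things at once: how often patients are admitted, and how long they are watched. If treatment delays PFS2, the treated arm accrues more admissions at an unchanged admission rate, and a true reduction in the rate could be masked.

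The objective is to describe and evaluate resource use associated with treatment, and SAP 4.2.12 directs the tables to payers. They should be readable without the reader having to guess at follow-up.

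A smaller point concerns scope. The list in SAP 4.2.12 covers admissions, stays and presenting symptom. It does not name the outpatient, physician or emergency visits that the endpoint and SAP 3.7 include.

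**Working it through.** The plan gives no figure for resource use, so there is none to reproduce. The question is how far an unadjusted count moves when the true admission rate is identical in both arms.

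**Inputs from the documents**
- Recruitment over 38 months (Protocol 9.2), taken as uniform.
- Latest trigger for the primary PFS analysis: 36 months after the last patient is randomized (Protocol 9.2), so month 38 + 36 = 74.
- Estimated first enrolment in Q3 2018 (Protocol synopsis) and SAP version 5 dated 20 December 2023, about month 63.
- PFS median 10 months on placebo, HR 0.65: 10/0.65 = 15.4 months. OS median 24 months, HR 0.73: 24/0.73 = 32.9 months. Both match Protocol 9.2.

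**Assumptions not in the documents**
- Exponential PFS2, placebo median 15 or 22 months, PFS2 HR 0.65 or 0.80.
- Cut at month 45 to 74.
- Constant admission rate, equal in both arms: 0.25, 0.5 or 1.0 per year.

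**Formulas.** Let λ = ln 2 / median, D = month of the cut, and r = monthly admission rate.

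Mean observation = (1/λ) × [1 − (e^(−λ(D−38)) − e^(−λD)) / (38λ)].

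Share ever admitted = r/(r+λ) × [1 − (e^(−(r+λ)(D−38)) − e^(−(r+λ)D)) / (38(r+λ))].

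Expected admissions per patient are r × mean observation, so the between-arm ratio does not depend on r.

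**Worked case: placebo median 15, HR 0.65, D = 45**
- Placebo: λ = 0.04621. Mean = (1/0.04621) × [1 − (0.7236 − 0.1250)/1.756] = 14.3 months.
- Durvalumab: λ = 0.03004. Mean = (1/0.03004) × [1 − (0.8104 − 0.2588)/1.141] = 17.2 months.
- Ratio 17.2/14.3 = 1.21.
- At 0.5 admissions per year, the share ever admitted is 40.0% versus 46.0%.

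**Ratio of mean observation, and so of admissions per patient**

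| Placebo median, HR | Month 45 | Month 55 | Month 63 | Month 74 |
|---|---|---|---|---|
| 15, 0.65 | 1.21 | 1.26 | 1.30 | 1.35 |
| 15, 0.80 | 1.11 | 1.14 | 1.15 | 1.18 |
| 22, 0.65 | 1.15 | 1.19 | 1.22 | 1.26 |
| 22, 0.80 | 1.08 | 1.10 | 1.12 | 1.14 |

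Over the same grid, the difference in share ever admitted runs from 1.9 points (median 22, HR 0.80, month 45, 0.25 per year: 27.8% versus 29.8%) to 9.8 points (median 15, HR 0.65, month 74, 0.5 per year: 46.8% versus 56.6%), from unrounded shares.

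**Cross-check with the plan's own design values** (follow-up uniform on 36 to 74 months)
- If the HOSPAD window behaved like PFS, mean observation would be 20.1 versus 14.0 months, ratio 1.43.
- If it behaved like OS, 32.2 versus 27.2 months, ratio 1.18.
- PFS2 times should generally fall between PFS and OS, so these are guides to the size and not strict bounds on the ratio.

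**Two limiting results.** If PFS2 is equal in the arms, the ratio is 1.00. With patient-time in the denominator, both arms return the same rate (50 per 100 patient-years at 0.5 per year) in every case.

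**The case against.** **The driver is PFS2, not progression-free time.** A reader might infer that a PFS benefit by itself inflates the durvalumab counts. The documents do not support that. Collection continues past first progression, and a PFS gain with equal PFS2 gives no distortion. This stands.

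**Nothing in the SAP says the counts must be unadjusted.** The list of statistics is open-ended and does not forbid a rate, and a Payer Analysis Plan may add one. This stands in part. The absence of adjustment is inferred from silence, and what payers will finally receive cannot be judged from these documents. But the additional analyses are optional and that plan is not available here, so it does not repair the tables that SAP 4.2.12 itself specifies.

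**Much of the list is not exposed.** Length of stay is described among people admitted, and presenting symptom is a descriptor. Neither scales directly with observation time. This stands; the point is confined to counts, per-patient means and the share ever admitted.

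**The visit types are not lost.** A reader might infer that outpatient and emergency use is dropped from the study. It is not: SAP 3.7 captures physician visits, emergency room visits and day cases, and Protocol 9.5.1.10 names outpatient and day-case contacts. What remains is that SAP 4.2.12 names none of these visits and neither analysis section names emergency visits.

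**The magnitude is not anchored, and a rate has its own weakness.** PFS2 medians, the PFS2 HR and admission rates are assumptions. A rate per patient-year also averages over periods when admissions may cluster, for example around early toxicity or near progression. Cumulative use per patient is a legitimate payer quantity. All of this stands, and it is why the raw counts should stay beside the rates.

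**Conclusion.** The point holds in a limited form. SAP 4.2.12 specifies admission summaries with no observation time for a module whose collection window is closed by efficacy events. If PFS2 differs between arms, admissions per patient would be about 8–35% higher in the arm with later PFS2, and the share ever admitted about 2–10 percentage points higher, with no true difference in admission rate. Equivalently, a true rate reduction of roughly 7–26% (1 − 1/1.08 to 1 − 1/1.35) would be hidden in the count. These sizes rest on the assumptions listed above.

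It would go too far to conclude that durvalumab will look more resource-intensive to payers. That requires a PFS2 difference, which the documents do not assume, and a Payer Analysis Plan that adds nothing.

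The objective is exploratory and descriptive, carries no alpha and may be reported outside the CSR. No efficacy or safety conclusion changes. This is a desirable improvement, not a necessary correction.

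**What to change.** In SAP 4.2.12:

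1. Define HOSPAD observation time for each patient as randomization to the earliest of PFS2, death, study termination or DCO.
2. By arm, beside the raw counts, report admissions, outpatient/physician visits and emergency visits per patient-year of that time.
3. Name outpatient/physician and emergency visits in the list of summaries, so that it matches the endpoint in SAP 1.1.4, the variables in SAP 3.7 and the outpatient and day-case contacts in Protocol 9.5.1.10.

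The cost is SAP wording, one derived variable built from dates the SAP already uses, and a little programming. No new data are collected, and alpha and the primary analyses are unaffected. Keeping the raw counts covers the case where the admission rate is not constant over time.
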